IRB Study Number: 20190760
Version: 10 Date: 06/06/2022

Title: Expressing Personal Recollections in English or Spanish to Alleviate Traumatic Emotions (Exprésate)

Protocol Number: 20190760

Protocol Version: 10

Protocol Date: 06/06/2022

PI Name: [name].

NCT number: NCT05090839

IRB Study Number: 20190760
Version: 10 Date: 06/06/2022

1) Protocol Title

Expressing Personal Recollections in English or Spanish to Alleviate Traumatic Emotions (Exprésate)

2) IRB Review History

This study protocol has not been previously submitted for review by an external IRB.

3) Study Objectives

Participants will be recruited from the greater Miami-Dade area via flyer and chain referral. This study aims to recruit 36 Latinas with a history of trauma into one of 3 separate arms of an augmented 4-week written emotional disclosure (WED) intervention: (1) Spanish-only, (2) English-only, and (3) non-trauma daily event writing in Spanish. This study seeks to test the hypothesis that WED regarding traumatic experience in one's primary, i.e., Spanish, language will be associated with more positive health outcomes than English WED or non-trauma related writing in Spanish. Collected prior to and after this intervention will be biomarkers, neurocognitive, psychiatric, sociocultural, and neuroimaging data to address the following study objectives:

To determine whether in Latinas with or without HIV exposure to an expressive writing intervention in Spanish will have an effect on primary study outcomes, i.e., changes in verbal learning & memory as well as symptoms of post-traumatic stress.

To determine whether exposure to an expressive writing intervention, delivered in either English vs. Spanish will have an effect on secondary study outcome biomarkers that are linked to cognitive and emotional functioning, i.e., changes in task and resting state functional brain activity and connectivity and stress hormone reactivity.

To explore whether intervention-related changes in primary and secondary outcomes is associated with changes in gene expression of transcription factors associated with brain glucocorticoid as well as peripheral inflammation-immune activation.

IRB Study Number: 20190760

Version: 10 Date: 06/06/2022

4) **Outcome Measures**

a) Primary Outcome(s)

Title: Change in PTSD symptoms as assessed by the Impact of Event Scale

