Description: 22-item self-report instrument that corresponds to DSM-IV symptoms of PTSD over last 7 days on a scale from 0 (not at all) to 4 (extremely).
Time Frame: Pre-intervention (Session 1) and at post-intervention (Session 6)

Title: Change in verbal learning as assessed by Hopkins Verbal Learning Task
Description: Measures verbal learning and memory function. (Three immediate recall trials) (0 no words recalled - 12 all words recalled).
Time Frame: at post-intervention (Session 6)

b) Secondary Outcome(s)

Title: Change in functional connectivity of the Default Mode Network (DMN).
Description: DMN is a large scale network of interacting brain regions implicated in emotion and memory. Activity/connectivity indexed by Fisher's Z or Beta wt.
Time Frame: Pre-intervention (Session 1) and at post-intervention (Session 6)

Title: Change in salivary measures of stress reactivity.
Description: 200 μ L of saliva will be used for immunoassay of alpha amylase (sAA) and adrenal corticotrophin releasing hormone (ACTH).
Time Frame: Pre-intervention (Session 1) and at post-intervention (Session 6)

c) Exploratory Outcome(s)

Title: Change in gene expression of inflammatory immune function.
Description: A peripheral blood sample will be used for immunoassay of NF- κ B p65 which is a transcription factor for a gene that controls inflammatory cytokine expression in peripheral white blood cells.
Time Frame: Pre-intervention (Session 1) and at post-intervention (Session 6)

Title: Change in gene expression of glucocorticoid activity.
Description: A peripheral blood sample will be used for immunoassay of FKBP5 which is a transcription factor for a gene that controls co-chaperone that modulates glucocorticoid receptor activity in response to stress in brain & body.
Time Frame: Pre-intervention (Session 1) and at post-intervention (Session 6)

5) **Background**

Trauma and neurocognitive function. Post-traumatic stress disorder (PTSD) and its symptoms of emotional numbing, intrusion, avoidance, and hyperarousal is three to

IRB Study Number: 20190760

Version: 10 Date: 06/06/2022

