have done “today from the time [they] woke in the morning.” These instructions will be modified slightly for three subsequent writing sessions to reflect descriptions of what they did on different days or what they planned to do on future days.

9) Study Timeline

The timeline will begin once the participant has signed the informed consent. Upon acquiring informed consent data will be collected during 6 separate time points. After the baseline session (1a & 1b) participants returned for the second study visit where they will be randomized to either the English trauma-writing intervention, the Spanish trauma-writing intervention or the daily-event-writing control. Experimental and control participants will be asked to visit their study based on their randomized assignment for a total of four occasions over a 4-week period so that they can engage in an online expressive writing exercise for 30 min. After each writing session, the writings will be submitted online to the researcher staff. All writings will be de-identified before being stored on secured UM servers and analyzed by study staff. Questionnaires, interviews, blood draws, neurocognitive assessments and neuroimaging data collected during session 1 were again administered 1 months after the end of each participant’s writing intervention. Upon completion of the session 6 participants involvement with the current study be complete and there will be no other study requirements.

10) Data Collection

Blood Assays. Approximately 50 ml of blood will be drawn from all participants, once at the first time point and up to 2 times (before and after neuroimaging session) at all subsequent time points. HIV-1 viral load and CD4 count will be recorded from each participant based upon the last labs drawn. Because menstrual cycle phase influence PTSD symptom presentation profile and psychophysiology (72, 73) data collection for all pre-menopause women will take place in the luteal phase and blood banked for ovarian steroid hormones, (e.g., estradiol). A salivary ACTH kit will be used to measure HPA-axis activity pre-scan and again following trauma recall. Peripheral GC sensitivity was tested by measuring in-vitro stimulated production of interleukin-6 (IL-6) in whole blood before and after cortisol vs. placebo application. Salivary cortisol will be analyzed using an Elisa plate reader at the Diabetes Research Institute under the supervision of [name].

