An abbreviated 15-item profile of mood states (POMS) questionnaire will be adapted to Spanish based on norms and factor structure reported in Hispanic/Latino populations (74) at the conclusion of each trauma session to assess levels of distress. Subjects will also complete a battery of self-report measures of PTSD symptom severity, subject Unit of Distress ,(impact of events scale—revised, IES-R (75), anxiety (the Spielberger State and Trait Anxiety Scales and Anxiety Sensitivity Index (ASI) (76), depression (Beck Depression Inventory, (BDI-II) (77), alexithymia (Toronto Alexithymia Scale-20, TAS-20 (78), multidimensional interoceptive awareness Scale, and dissociation using the Dissociative Experiences Scale -2 (DES-II) (79), early trauma (Early Trauma Inventory, (ETI) (80), Perceived Support Network Inventory, and Brief COPE. Surveys that have been translated and are archived by CLaRO will also be included, such as measures of psychological symptomatology (Brief Symptoms Inventory (BSI) (81) depression (The Center for Epidemiological Studies Depression Scale (CESD) (82) anxiety (General Anxiety Disorder Scale (GAD-7) (83)) and intimate partner violence (HITS Tool for Intimate Partner Violence Screening (HITS) (84). The Physical Symptoms Questionnaire (PHQ-15), Pittsburgh Sleep Quality Index (PSQI) and Patient Health Questionnaire (PHQ) will also be administered. To assess HIV-associated neurocognitive dysfunction a neurocognitive battery will be administered and performance compared with published age- and education-adjusted normative data to calculate z scores (NPZ), within several cognitive domains. These domains include global functioning (Trail Making Test (TMT), Hopkins Verbal Learning Task, Brief Visual Memory Test, WAIS-R Digit symbol substitution, WAIS-R Digit Span, WAIS-R letter number sequencing, WAIS-R Design Block Test, COWAT (Spanish), Paced Auditory Serial Addition Test, Rey Complex Figure Test, Verbal Fluency Task, Stroop Color-Word Interference Test, Grooved Pegboard, and Iowa Gambling Task. Anti-retroviral regimen will be assessed with the Adult (ACTG) structured interview (69). Health Markers for Review of Systems, Basic Demographic Questionnaire, Pittsburgh Sleep Quality Index, and Physical Health Questionnaire. Individuals randomized to the S-WED group will be prompted to self-report in Spanish i.e., (anger or “enojo”, anxiety or “ansiedad” and depression or “tristeza”. Note: “arrepentido por cosas hechas”= regret about things done, desanimado= unmotivated, inútil= helpless, aterrorizado= terrorized, and culpable= guilty”. Pronoun use will also be quantified from their responses, as research suggests that trauma victims that use more first person singular pronouns (e.g. I/mine, “yo/mio”) in trauma narratives have worse, long-term symptom severity(86)), which extend to broader use of singular pronoun use (87). A similar pattern was observed in depressed and negative mood individuals (84).

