	*Self/other- compassion scales		X					X
	External and Internal Shame Scale (EISS)		X					X
	*HITS Intimate Partner Violence Screening Tool		X					X
	Religion & Spirituality Questionnaire		X					X
	Profile of Mood States		X	X	X	X	X	X
Neurocognitive	Trail Making Test		X					X
	Hopkins Verbal Learning Task		X					X
	Brief Visual Memory Test		X					X
	WAIS-R Digit Symbol Substitution		X					X
	WAIS-R Digit Span		X					X
	WAIS-R Letter Number Sequencing		X					X
	WAIS-R Block Design Test		X					X
	COWAT		X					X
			X					X
	Paced Auditory Serial Addition Test		X					X
	Rey Complex Figure Test		X					X
	Verbal Fluency Task		X					X
	Color-Word Interference test		X					X
	Grooved Pegboard		X					X
	Iowa Gambling Task		X					X
Behavioral	Adult (ACTG) structured interview		X					X
	Self-compassion task		X					X
Biomarker	Saliva for CORT or ACTH & sAA via ELISA		X					X
	Serum and plasma for NFkB & FBPK5		X					X
	Serum and plasma aliquots for storage		X					X

IRB Study Number: 20190760

Version: 10 Date: 06/06/2022

Health Markers							
	Review of systems		X				X
	Basic Demographic Questionnaire		X				X
	Pittsburgh Sleep Quality Index		X				X
	Physical Health Questionnaire		X				X

11) Specimen Banking*

Participants will be asked to abstain from illicit recreational substances, caffeinated and decaffeinated substances, aspirin and other medications, alcohol and strenuous exercise, and to fast from 10 pm on the night before arrival to the Behavioral Medical Research Center (BMRC) between 8 and 10 am before each visit. Participants will be advised to consult their physician before beginning the fast if the schedule varies from normal eating patterns. On the first visit, a urine toxicology screen (i.e., alcohol, barbiturates, benzodiazepines, LSD, PCP, THC, morphine, and amphetamines) will be performed. Urine samples will not be stored after analysis.

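### Self-report language is tied to the randomised arm for at least the mood ratings, and no arm-independent test language is set for the IES-R or HVLT, so confounding of the Spanish v English comparison is not ruled out

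*Combined protocol and SAP*

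**What the plan says.** Section 3 (Study Objectives) puts the study's expectation as follows: "WED regarding traumatic experience in one's primary, i.e., Spanish, language will be associated with more positive health outcomes than English WED". Daily-event writing is the second comparator. Language is thus the experimental factor that separates the two disclosure arms.

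Section 4 names two primary outcomes: "Title: Change in PTSD symptoms as assessed by the Impact of Event Scale" and "Title: Change in verbal learning as assessed by Hopkins Verbal Learning Task". Neither entry states a language of administration. Table 1 schedules both measures at T1 and T6, again without a language.

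The Neuropsychological assessment paragraph in section 10 lists the whole battery, with the IES-R among the self-report measures. Near its end it states: "Individuals randomized to the S-WED group will be prompted to self-report in Spanish". The illustrations are mood terms: anger, anxiety and depression with their Spanish equivalents, then a note that includes "desanimado= unmotivated, inútil= helpless, aterrorizado= terrorized, and culpable= guilty". Earlier in the paragraph, "An abbreviated 15-item profile of mood states (POMS) questionnaire will be adapted to Spanish"; Table 1 places this scale at every visit from T1 to T6. The COWAT is marked as Spanish, the PCL-C as Spanish-English, and a few surveys as already translated. The IES-R and the "Hopkins Verbal Learning Task" carry no such label.

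On timing, section 9 says: "After the baseline session (1a & 1b) participants returned for the second study visit where they will be randomized". On eligibility, inclusion criterion 4 in section 6 admits bilingual women as well as Spanish speakers or English speakers. The analysis paragraph in section 12 specifies linear mixed models and mentions no term for test language.

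**The concern.** Where the treatment contrast is itself a contrast of languages, the language of measurement has to be independent of arm. Otherwise a difference between S-WED and E-WED at Session 6 could come from the writing, from the language of the test, or from both. The HVLT scores recalled words and the IES-R is a worded symptom scale, so both could plausibly shift with language.

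The eligibility rule leaves no default: a bilingual woman could be assessed in either language, and someone must choose at each visit. The only written rule on the language of self-report points to the arm. If staff extend it to the IES-R, or follow the same habit for the HVLT, language and arm become aligned. Randomisation does not balance this away, because the alignment is created after randomisation. If the alignment is complete, no covariate can separate the two effects at analysis.

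**Working it through.** **1. What the sentence covers.** It concerns self-report, names no scale and no visit, and is illustrated only with mood words.
- Mood-type ratings such as the POMS: covered on any reading.
- IES-R: a self-report scale in the same paragraph, so covered on a broad reading but not named.
- HVLT: a performance test, so not covered. No other passage sets its language.
- E-WED and control women: no rule.

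**2. When the rule could act.** Randomisation comes after Session 1, so an arm-linked rule cannot operate at baseline. It can operate from Session 2 onward, including Session 6. Let b be the mean shift in a score caused by test language in one arm relative to the other, absent at Session 1 and present at Session 6. The expected difference in change is then

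(treatment effect + b) − 0 = treatment effect + b.

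Subtracting baseline does not remove b.

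**3. Size, for illustration.** The documents give no language effect, SD, alpha or power for the clinical outcomes, and the total of 36 has no derivation beyond 24 + 12 = 36. The following are therefore assumptions:
- an equal split of the 24 disclosure women, 12 v 12 (section 8 gives only the 24);
- a two-sided 5% two-sample t-test, as a stand-in for the planned mixed model;
- b of 0.2, 0.3 or 0.5 SD of the analysed score;
- a true treatment effect of zero.

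Standard error of the difference = √(2/12) = 0.408 SD. Degrees of freedom = 22, critical value 2.074. Non-centrality = b / 0.408. The rejection rate is the two-tailed non-central t probability beyond ±2.074.

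| b (SD) | Non-centrality | All women tested in arm's language | Half of them (mean shift b/2) |
|---|---|---|---|
| 0 | 0 | 5.0% | 5.0% |
| 0.2 | 0.49 | 7.6% | 5.6% |
| 0.3 | 0.73 | 10.8% | 6.4% |
| 0.5 | 1.22 | 21.6% | 9.0% |

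**4. Change scores.** If b is in cross-sectional SD units and enters only at Session 6, the SD of the change is √(2(1 − r)), where r is the pre-post correlation (also assumed). For b = 0.3:
- r = 0.5: SD 1.00, shift 0.30, rejection 10.8%
- r = 0.7: SD 0.775, shift 0.39, rejection 14.8%
- r = 0.8: SD 0.632, shift 0.47, rejection 19.9%

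A stronger pre-post correlation makes the same language shift more visible, because it reduces the noise and leaves the bias.

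**5. After the fix.** With one language per woman, set before randomisation and kept at Session 6, the arm-linked shift is zero and the rate returns to 5.0%.

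**The case against.** The best counter-case is that the sentence is narrow. Its content is listed as mood words only, and the next sentence turns to pronoun use in the women's responses, which suits mood ratings or narratives better than a 22-item scale scored 0 to 4. No visit is named, so the rule might apply only during the writing sessions. The POMS is neither a primary nor a listed secondary outcome. Language versions may also be settled in the forms that section 10 says the IRB approved, which are not part of these documents.

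Much of this stands. A reader might infer that both primary outcomes are confounded by design, or that the HVLT will favour S-WED because E-WED women are tested in a weaker language. The documents do not support either inference. The HVLT is not self-report and nothing links its language to arm. Nothing says that E-WED women are tested in English. Spanish is described as the primary language, but eligibility also admits English speakers, so Spanish need not be every woman's stronger language. For the IES-R no direction can be argued at all.

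The narrow reading still leaves a gap: it sets no test language for either primary outcome and nothing to prevent an arm-linked choice. The broad reading is not far-fetched, because the section on trauma recall in the scanner expressly matches prompt language to the randomised group. Approved forms could supply translations, but they would not by themselves say which woman receives which version at which visit.

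**Conclusion.** The point holds as an uncontrolled route to bias. Arm-linked language is explicit for mood-type self-report, possible for the IES-R at Session 6, and neither stated nor prevented for the HVLT. Confounding of the Spanish v English comparison is therefore not ruled out, but it is not established, and its direction and size cannot be determined from the documents.

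The range of 7.6% to 21.6% shows only what would follow if every woman were tested in her arm's language and that shifted scores by 0.2 to 0.5 SD; with half the women affected it is 5.6% to 9.0%. Firm conclusions rest on two facts in the text: randomisation comes after baseline, and no arm-independent language rule exists for either primary outcome. Because language is the experimental factor, this is more than a missing detail.

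**What to change.** - In section 10, limit the arm-linked self-report sentence to the writing sessions (Sessions 2 to 5) and name the measures it covers.
- Add a rule such as: The language of the IES-R, the other self-report scales, the HVLT and the other verbal tests is set for each woman at Session 1, before randomisation, and the same language is used at Session 6 whatever her arm. The basis could be stated preference, or the BASH or BAS already scheduled at T1; if a scale is used, give the scoring rule.
- Record the language used for each assessment and report it by arm and visit, with any departures. A sensitivity analysis with test language in the mixed model is then possible, provided that language does not coincide with arm.

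The cost is a few sentences and one recorded field. The small downside is that some women will complete scales in a language other than the one they wrote in.
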